#### 5.2.6 Visit 6a (Month 6/Wk 26 [ $\pm 3$ wk]) and Visit 8a (Month 12/Wk 52 [ $\pm 1$ wk]) – MOD-4023 Arm Only

Visit 6a and 8a will be conducted on dosing day before dosinga, for MOD-4023 arm patients only. The following assessments will be conducted at the study site or at the patient home (if allowed according to local regulations):

- MOD-4023 serum levels.
- Anti-MOD-4023 Ab.
- AEs and local tolerability (aligned with Appendix H) assessment.
- Concomitant medication recording aligned with the questionnaire in [Appendix I](#).

#### 5.2.7 Visit 6b (Month 6/Wk 26 [ $\pm 3$ wk]) – MOD-4023 Arm Only

Patients in the MOD-4023 arm will be requested to inject the study drug during the day/night at their convenience and come to the study site at 7-12 hours post-dose for ECG assessment.

Visit 6a and 6b may be combined and conducted on the same date; in such case, the patient will inject the study drug at the study site following blood samples collection and will come back for ECG measurements (Visit 6b) 7-12 hours post dosing.

#### 5.2.8 Visit 9 (Month 13/Wk 56 ( $\pm 5$ days)) – Only for patients not continuing on into the OLE study

Patients not continuing in the OLE study will be contacted 30 days ( $\pm 5$  days) after Visit 8 (inclusive of 8a) in order to obtain safety related information (see questionnaire in Appendix I).

a These visits can be done on any dosing day within the visit window.

### 5.3 LT-OLE PERIOD (VISITS 10 TO 16)

After completion of 12 months treatment in the main study and continuing to meet the LT-OLE inclusion/exclusion criteria of this protocol, patients will be eligible to rollover into a single arm LT-OLE treatment period with MOD-4023. An informed consent/assent will be obtained from patients and/or parent/s or legal/authorized guardian as required per local regulation.

Patients who received MOD-4023 during the main study will continue with the same dose of MOD-4023 (mg/kg/wk), adjusted for body weight. For these patients, study visits will take place every three months on Day 4 (-1) post-dose. These patients will consent to the LT-OLE preferably during Visit 7 of the main study to ensure availability of MOD-4023 at their next visit. If necessary, informed consent can be obtained at Visit 8 main study/10 LT-OLE. These Patients will continue treatment at Visit 8/10, skip Visits 9 and 11 and have a telephone visit at Visit 12 (one month post LT-OLE entry (Month 13 [ $\pm 2$ wk])).

Patients who received Genotropin®, during the main study will be switched to MOD-4023 starting no less than one day [ $+2$ wk] after cessation of Genotropin® treatment. Recommended injection days are indicated in Appendix E. These patients will consent to the LT-OLE preferably during Visit 7 of the main study to ensure availability of MOD-4023 at their next visit. If necessary, informed consent can be obtained at Visit 8/10. Patients will begin treatment with MOD-4023 at Visit 8/10, skip Visit 9 and have additional onsite visits at Visit 11 (Month 12, Day 10 post first MOD-4023 dose [ $10+4$  days]) and Visit 12 (one month (Month 13 post first MOD-4023 dose [ $\pm 2$ wk])). All Patients will be provided with a diary card.

For all patients switching from Genotropin® to MOD-4023, the following will also be done:

- MOD-4023 will be dispensed based on patient weight at a starting dose of 0.66 mg/kg/wk.
- Training on and administration of MOD-4023 using the device.
- Local tolerability after first dose administered at site.

Patients who experience a delay for any reason between completion of the main study and entry into the LT-OLE may have to temporarily stop treatment. If initiation/re-initiation of treatment occurs less than 90 days after Visit 8 only training on and administration of MOD-4023 and local tolerability after first dose administered at site is required.

Patients who are off treatment for more than 90 days due to technical reasons e.g. delay in approval of Protocol Amendment may be allowed to continue into the LT-OLE after confirmation of availability of all required baseline LT-OLE assessments (Visit 8/10). The following tests and assessments must be repeated:

- Safety laboratory tests: chemistry, hematology and urinalysis.
- Parameters of glucose metabolism: overnight fasting glucose, overnight fasting insulin, HbA1c.
- Assessment of anti-MOD-4023 Ab for all patients (Genotropin® group – baseline for future tests).
- Assessment of biochemical markers: IGF-1, IGF-1 SDS, IGF-BP-3 and IGF binding protein-3 (IGFBP-3) SDS serum levels.

5.3.1 Visit 11 (Month 12, Day 10 [+4days] post first MOD-4023 dose) for patients switching from Genotropin® to MOD-4023 only

The following assessments will be conducted at the study site or at the patient's home (if allowed according to local regulations):

- MOD-4023 serum levels.
- Anti-MOD-4023 Abs.
- AEs and local tolerability (aligned with Appendix H) assessment.
- Concomitant medication recording aligned with the questionnaire in [Appendix I](#).

5.3.2 Visit 12 (one month post first MOD-4023 dose(Month 13 [ $\pm 2$ wk])) will be performed on site for patients switching from Genotropin® to MOD-4023

The following assessments will be conducted at Visit 12 on Day 4 (-1) post dose:

- AEs, local tolerability, and concomitant medications.
- Overall health status assessment, including complete physical examination and vital signs.
- Urine pregnancy test once a female patient reports first menstrual cycle (menarche).
- Safety laboratory tests: chemistry, hematology and urinalysis.
- Assessment of biochemical markers: IGF-1, IGF-1 SDS, IGFBP-3 and IGFBP-3 SDS serum levels.
- Fundoscopy (ONLY if there are signs or symptoms indicative of benign intracranial hypertension).
- MOD-4023 serum levels.
- Anti-MOD-4023 Abs.
- Fundoscopy (ONLY if there are signs or symptoms indicative of benign intracranial hypertension).
- Return of used and unused injection devices to the site and diary card.
- Drug dispensing and accountability.

Existing MOD-4023 patients will have a telephone visit at Visit 12 (one month post LT-OLE entry [Month 13  $\pm 2$ wk]) to ask about AEs, local tolerability and concomitant medications. This visit will be completed using the questionnaire in Appendix I.

5.3.3 Visit 13 (Month 15/Wk 65 [ $\pm 2$ wk]), Visit 14 (Month 18/Wk 78 [ $\pm 2$ wk]), Visit 15 (Month 21/Wk 91 [ $\pm 2$ wk]), Visit 16 (Month 24/Wk 104 [ $\pm 4$ wk])

During the first year of LT-OLE, the following assessments will be conducted every three months on day 4 (-1) post-dose for all patients:

- Auxology measurements: Actual height (average of three consecutive measurements) measured on a calibrated wall mounted stadiometer.
- Overall health status assessment, including complete physical examination and vital signs assessment.
- Individual dose adjustment based on weight.
- AEs, local tolerability, and concomitant medications.

Effective Date: Date of final electronic approval

- Urine pregnancy test at every visit once a female patient reports first menstrual cycle (menarche).
- Assessment of biochemical markers: IGF-1, IGF-1 SDS, IGFBP-3 and IGFBP-3 SDS serum levels.
- Assessment of MOD-4023 serum levels.
- Assessment of anti-MOD-4023 Ab.
- Fundoscopy (if there are signs or symptoms indicative of benign intracranial hypertension).
- Return of used and unused injection devices to the site and diary card.
- Drug dispensing and accountability.

The following assessments will also be conducted at Visit 13 (Month 15), Visit 14 (Month 18) and Visit 16 (Month 24) on day 4 (-1) post-dose visits:

- Safety laboratory tests: chemistry, hematology and urinalysis.
- Assessment of thyroid function: TSH, FT4.
- Parameters of glucose metabolism: overnight fasting glucose, overnight fasting insulin, HbA1c.
- Parameters of lipid metabolism: overnight fasting cholesterol, triglycerides, HDL, LDL, Lp(a), FFA.

The following assessments will also be conducted at Visit 16 (Month 24) on day 4(-1) post-dose:

- ECG.
- Bone age.
- Pubertal status.
- For males that are 13 years and older: LH, FSH and testosterone. For females that are 12 years and older: LH, FSH and estradiol.

Collection of samples for MOD-4023 serum levels and anti-MOD-4023 Ab levels must be obtained on dosing day pre- dose. For the ECG that will be conducted at 7-12 hours post-dose patients will be requested to inject MOD-4023 during the day/night at their convenience and come to the study site at the requested timepoint for the ECG. Visits may be split to allow for pre-dose blood collection for serum levels and antibody tests and post-dose ECG or the patient will be asked to come to the study site for blood collection, administer the required dose, and return to the study site 7-12 hours post-dose.

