3. ENDPOINTS AND BASELINE VARIABLES: DEFINITIONS AND CONVENTIONS

3.1. Efficacy Endpoints

3.1.1. Annualized Height Velocity (cm/year)

AHV at each 12 month is based on the difference between the height (HT) at each 12 month and the height at the previous 12 month.

$$\text{HT at Month 12 of current year} - \text{HT at Month 12 of prior year}$$

AHV(cm/year) = -----
(Month 12 Visit Date of current year – Month 12 Visit Date of prior year) / 365.25

The following algorithm will be used in case the reference visit (i.e., previous 12 month visit) is missing:

- If main period Month 12 (OLE Baseline), Visit 16 (OLE Month 12), Visit 20 (OLE Month 24), Visit 24 (OLE Month 36) are not missing, these will serve as reference visits.
- If missing, create anchor visit which is the scheduled visit (non-missing) prior to the missed reference visit, or scheduled or unscheduled visit (non-missing) after the missed reference visit based on the anchor logic described below:
 - A subject showed a missing reference visit at visit 16
 - This subject completed Visit 15 (OLE Month 9; Anchor A) and Visit 17 (OLE Month 15; Anchor B) and did not complete an Unscheduled Visit. One of the scheduled visits (non-missing) will be determined as the Anchor Visit
- Anchor logic:
 - If Anchor B – Anchor A < 6 months (180 days) then Anchor A will be used as the reference visit.
 - If Anchor B – Anchor A \geq 6 months (180 days) then Anchor B will be used as the reference visit.
 - If a reference visit was performed out of window and reported as an unscheduled visit then unscheduled visit will be used as the reference visit, Anchor C.

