Appendix 2. Data Derivation Details

Appendix 2.1. Definition and Use of Visit Windows in Reporting

Annual ADA characterization will be performed based on the algorithm below using visit windows as applied to ADPC dataset.

Period	From	To
Main	Day 2 (main dosing +1)	Day 410
OLE Year 1	Day 2/OLE Baseline (OLE dosing +1)	Day 410 (OLE Month 12)
OLE Year 2	Day 411	Day 774
OLE Year 3	Day 775	Day 1138
OLE Year 4	Day 1139	Day 1502

The following table will provide the adverse events reporting period to a given study period.

Period	From	To	AE linking to study period
Main	On or post first Main dosing date/time (in exposure dataset)	Prior to the first OLE dosing date/time	If the new AE strictly starts between the start and end dates of a given period, it will be counted in that period.
OLE Year 1 (visit13 -16)	On or post first OLE dosing date/time (defined in exposure dataset)	Visit 16 end date; if Visit 16 is missing, then first OLE dosing date + 365	
OLE Year 2 (visit 17-20)	“OLE Year 1 To” date + 1	Visit 20 end date; if Visit 20 is missing, then “OLE Year 2 From” date + 365	
OLE Year 3 (visit 21-24)	“OLE Year 2 To” date + 1	Visit 24 end date; if Visit 24 is missing, then “OLE Year 3 From” date + 365	
OLE Year 4 (visit 25-28)	“OLE Year 3 To” date + 1	Visit 28 end date; if Visit 28 is missing, then “OLE Year 4 From” date + 365	

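### OLE Year-1 height velocity runs from the main-study Month 12 height even after a treatment gap, so for delayed children it mixes off-drug and on-drug time

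*Protocol*

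**What the plan says.** **Protocol 5.3 (LT-OLE period).** Children delayed between the main study and the extension "may have to temporarily stop treatment". If treatment starts or restarts less than 90 days after Visit 8, only device training, administration and a local tolerability check are required. A separate paragraph covers "Patients who are off treatment for more than 90 days due to technical reasons", with delayed approval of an amendment as its example. They may enter "after confirmation of availability of all required baseline LT-OLE assessments (Visit 8/10"). Then: "The following tests and assessments must be repeated", followed by safety laboratory tests, glucose metabolism, anti-MOD-4023 antibodies and IGF-1/IGFBP-3. Height is not listed for either group, and no maximum gap is stated.

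**SAP 3.1.1.** AHV is the height difference between two yearly visits divided by the time between their dates. Main-study Month 12 is labelled OLE Baseline and is the Year-1 reference if not missing. The substitute rules, including the one for unscheduled visits, are introduced by "The following algorithm will be used in case the reference visit (i.e., previous 12 month visit) is missing".

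**Elsewhere in the SAP.** Section 2.1.1 adopts a treatment-policy strategy for children who entered the OLE and received at least one dose. Section 5.1 plans no hypothesis test. Section 6.1.2 gives sensitivity and supplementary analyses as not applicable. Appendix 2.1 starts the adverse-event Year 1 "On or post first OLE dosing date/time (defined in exposure dataset").

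**The concern.** A delayed child has completed Visit 8, and Protocol 5.3 asks for confirmation that the Visit 8/10 baseline assessments are available. The Month 12 height is therefore normally present, and the substitute rules in SAP 3.1.1 do not come into play. The Year-1 numerator and denominator both begin at Visit 8, although extension treatment begins later. Nothing in either document removes the gap, excludes these children or takes a new reference height.

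Protocol 8.6.5 gives the purpose of the extension analysis as reporting the effect of long-term treatment on annual height velocity, and SAP 5.3 calls AHV the primary endpoint. Year 1 is the first extension result and, for children switched from Genotropin, the first year on somatrogon. If off-drug growth is slower, Year 1 looks low for a reason unrelated to the drug and Year 2 looks better by comparison. If gaps were more common in one original arm, the by-arm summaries in SAP 6.1.1 would be affected unequally; the documents do not say whether they were.

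**Working it through.** The plan states no figure on this point, so there is nothing to reproduce. The check is a time-weighted average.

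**Inputs from the documents**
- Gap *g*: more than 90 days, no limit (Protocol 5.3). Shorter gaps are also possible.
- Visit 8 at Week 52 (Protocol 5.2) and Visit 16 at Week 104 (Protocol 5.3.3): 52 weeks, or 364 days, apart.
- AHV divisor: time between visit dates (SAP 3.1.1).

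**Inputs assumed (not in the documents)**
- On-drug velocity 8 to 9 and off-drug velocity 4 to 5 cm/year, so the difference *d* runs from 8 − 5 = 3 to 9 − 4 = 5 cm/year.
- Velocity after restart is the same as it would have been without the gap.

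**Formula.** Reported AHV = on-drug velocity − *d* × (*g* / *T*), where *T* is the interval from Visit 8 to Visit 16. The documents do not say how Visit 16 is timed for a late entrant, so both cases are shown:
- restart clock (Visit 16 at 52 weeks after the first OLE dose): *T* = 364 + *g*
- fixed clock (Visit 16 stays at Week 104): *T* = 364

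**Off-drug share.** This needs no velocity assumption. For a 90-day gap it is 90/454 = 19.8% (restart clock) or 90/364 = 24.7% (fixed clock).

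**Shortfall for one child (cm/year)**

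| Gap | Clock | Share *g*/*T* | *d* = 3 | *d* = 5 |
|---|---|---|---|---|
| 60 days | restart | 60/424 = 14.2% | 0.42 | 0.71 |
| 60 days | fixed | 60/364 = 16.5% | 0.49 | 0.82 |
| 91 days | restart | 91/455 = 20.0% | 0.60 | 1.00 |
| 91 days | fixed | 91/364 = 25.0% | 0.75 | 1.25 |
| 180 days | restart | 180/544 = 33.1% | 0.99 | 1.65 |
| 180 days | fixed | 180/364 = 49.5% | 1.48 | 2.47 |

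Hand check at 8 on and 4 off drug with a 91-day gap: restart clock (8 × 364 + 4 × 91)/455 = 7.2; fixed clock (8 × 273 + 4 × 91)/364 = 7.0.

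**Group mean.** Shift = share of children affected × shortfall. The share affected is not given, so these are illustrations:
- 5% affected, 91 days: 0.03 to 0.05 (restart) or 0.04 to 0.06 (fixed)
- 10% affected, 91 days: 0.06 to 0.10 or 0.075 to 0.125
- 10% affected, 180 days: 0.10 to 0.17 or 0.15 to 0.25

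**Which clock is better supported?** Protocol 5.3 times Visits 11 and 12 for switchers from the first MOD-4023 dose, and Visit 12 for continuing children from LT-OLE entry. The antibody windows in SAP Appendix 2.1 count from OLE dosing to a day labelled OLE Month 12. These favour the restart clock. Protocol 5.3.3 prints Week 104, so the matter is not settled.

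**The case against.** **The extension is descriptive.** This stands. No test or type I error is involved, and the primary endpoint (Visit 2 to Visit 8) is unaffected. It limits severity. It does not remove the point, because where nothing is tested the summary is itself the result.

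**The size is assumed.** This also stands. Late entry is an exception for technical reasons, the usual route being to continue or switch at Visit 8/10. With few children affected, the shift is small beside the planning SD of 2.5 cm/year in Protocol 8.1. The largest figures above also need the less well supported fixed clock.

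**Treatment policy already covers it.** This stands in part. For children already on somatrogon the gap is an interruption of continuing therapy, and Protocol 5.3 itself speaks of re-initiation. Including that time is arguably what SAP 2.1.1 intends. It is harder to argue for Genotropin switchers, whose gap precedes any somatrogon. A reader might infer that the estimand rules the gap out for everyone; the text does not support so absolute a reading. Nor does it name the gap as an intercurrent event.

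**Adverse-event and antibody periods start at OLE dosing, but AHV does not.** A reader might infer that one of them must be wrong. Exposure-linked safety windows and visit-to-visit height intervals serve different purposes, so the difference alone is not an error.

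**Re-baselining has problems of its own.** This stands. A reference moved only above 90 days leaves an 89-day gap almost as affected. It also pools children starting Year 1 off drug with children on continuous growth hormone.

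**Conclusion.** The point holds at low to moderate severity. Protocol 5.3 and SAP 3.1.1, read together, place the off-drug gap inside Year-1 AHV, and no other provision in either document offsets it. The affected child's figure is probably too low: by 0.6 to 1.0 cm/year for a 91-day gap on the restart clock, or 0.75 to 1.25 if Visit 16 stays at Week 104. This rests on the assumed 3 to 5 cm/year difference and on unchanged growth after restart. The effect on the group mean cannot be determined from the documents.

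A reader might infer that untreated time is credited to somatrogon and inflates its effect. Under these assumptions the bias runs the other way, so it cannot create a false claim of long-term efficacy. Nor does the point bear on the non-inferiority conclusion. What it can distort is the level of Year 1 and its comparison with Year 2.

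**What to change.** Keep the treatment-policy summary as planned. In SAP 6.1.2, replace the not-applicable entry with:

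1. A supplementary Year-1 AHV summary, by original arm and in total, excluding children with an off-treatment gap between Visit 8 and the first OLE dose. Identify them from the exposure dataset. Count all gaps, and show the group above 90 days separately. State in the SAP which interval is ordinary rollover rather than a gap, since Protocol 5.3 already allows a window of up to two weeks for switchers.
2. The number and length of gaps, by original arm.
3. Where a height was recorded at restart, Year-1 AHV from that height and date, as a further supplementary result.

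The SAP should also say how Visit 16 is timed for late entrants.

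The cost is a little programming, a few sentences, and a slightly smaller N in the supplementary summary. It uses data already held. A mandatory restart height would be a protocol change requiring the submissions and approvals in Protocol 9.3, across about 200 sites. Because the protocol's own example of a gap is slow amendment approval, such a change could come too late for the children concerned. The fix does not depend on it.

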## 5.8 SAFETY ASSESSMENTS AND ENDPOINTS

Safety assessments will be based on changes from baseline of clinical AEs (including local tolerability, i.e. injection site reaction) reported by the patient or observed by the investigator, concomitant medication use, treatment compliance, vital signs, ECG, physical examination, fundoscopy and laboratory assessments (hematology, blood chemistry, glucose metabolism, lipid

a If not done with the central reader during the Screening visit.

metabolism, thyroid function, IGF-1 levels, immunogenicity and urinalysis). AEs and concomitant medication use will be assessed at every visit. Physical examination and safety laboratory assessments will be performed according to the schedule of events in Appendix A.

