### 5.8.9 Laboratory Assessments

All routine clinical laboratory assessments will be performed by central laboratory as provided in [Appendix K](#) according to the schedule in [Appendix A](#), other than urine pregnancy testing, when required, which will be conducted at the local laboratory. The laboratory evaluations will include:

1. Hematology: Red Blood Cell (RBC) count, hemoglobin (HGB), hematocrit (HCT), Mean Cell Hemoglobin (MCH), Mean Cell Hemoglobin Concentration (MCHC), Mean Corpuscular Volume (MCV), White Blood Cell (WBC) count and differential, platelet count, prothrombin time (PT)/international normalized ratio (INR), partial thromboplastin time (PTT) (if indicated only).
2. Serum chemistry: total protein, albumin, total bilirubin, alanine aminotransaminase (ALT), aspartate transaminase (AST), gamma-glutamyl transferase (GGT), lactate dehydrogenase (LDH), creatinine phosphokinase (CPK), alkaline phosphatase, sodium, potassium, calcium, phosphate, blood urea nitrogen (BUN), liver function test (LFT), creatinine.
3. Lipid metabolism: overnight fasting cholesterol, triglycerides, high density lipoprotein (HDL), low density lipoprotein (LDL), lipoprotein a (Lp(a)), Free Fatty Acids (FFA).
4. Glucose metabolism: overnight fasting glucose and insulin, HbA1C.
5. Thyroid function: TSH, FT4.
6. Immunogenicity: anti-MOD-4023 Ab (MOD-4023 arm only during the main study and all patients during the LT-OLE) and Abs to r-hGH (all patients). It is recommended that if the Genotropin patients normally administer their drug in the morning, that they wait on those visit days to administer the Genotropin® until after the blood sampling.
7. IGF-1, IGF-1 SDS, IGFBP-3 and IGFBP-3 SDS levels.
8. MOD-4023 serum levels (MOD-4023 arm only during the main study and all patients during the LT-OLE).
9. Urinalysis: pH, glucose, ketones, erythrocytes, leukocytes, protein.
10. Urine pregnancy test.
11. Luteinizing hormone (LH), Follicle-stimulating hormone (FSH) and testosterone (for males that are 13 years and older).
12. LH, FSH and estradiol (for females that are 12 years and older).

For further details on blood sample collection and shipment to the central laboratory, please refer to the Central Laboratory Manual.

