Local tolerability			X	X r	X	X	X	X	X	X	X s	X r	X t
Adverse events			X	X	X	X	X	X		X	X	X r	X t
Prior & concomitant medications	X		X	X	X	X	X	X		X	X	X r	X t
IP return					X	X	X			X	X		
Fundoscopy			ONLY if there are signs or symptoms indicative of benign intracranial hypertension										
MRI u , if possible with contrast or CT (if required) post GH stimulation	X												
Laboratory Assessments													
Hematology v , chemistry w , & urinalysis x	X		X		X	X	X			X	X		

r For MOD-4023 arm: assessment will be conducted at the clinic or at the patient's house (according to local regulations), for Genotropin® arm: by phone interview.

s For Genotropin injections and following administration of MOD-4023, as applicable.

t Phone interview, only for those patients who are not participating in the LT-OLE.

u Historical MRI or CT is permitted if within 12 months; MRI or CT which was conducted no more than 12 months prior to ICF signature data will be acceptable. For GHD associated with a congenital CNS defect, the MM could allow for use of the historic MRI or CT >12 months old.

v For the screening period, additional 4 wks might be added due to technicalities or patient's benign illness.

w Hematology: RBC Count; HGB; HCT; MCH; MCHC; MCV; WBC Count and Differential; Platelet Count, PT/INR, PTT (if indicated only).

xChemistry: total protein, albumin, total bilirubin; ALT, AST, GGT, LFT, LDH, CPK, alkaline phosphatase; sodium, potassium, calcium, phosphate; BUN, creatinine.

Effective Date: Date of final electronic approval

Study Procedure	Screening		Baseline	Treatment								Follow-up b	
				10 (+4)	4 (+1)	13 (±1)	26 (±1)	26 (±3)	26 (±3)	39 (±1)	EOS b		
Study Day (± in dy/s)	a -56 to -1		1/								52 (±1)	52 (±1)	56 (±5 days)
Study Wk (± in wk/s)	-8 to -1 (+4) a		0 (+4 from Eligibility)		4 (+1)	13 (±1)	26 (±1)	26 (±3)	26 (±3)	39 (±1)	52 (±1)	52 (±1)	56 (±5 days)
Study Month	-2		0	0.5	1	3	6	6	6	9	12	12	13
Study Visit	1		2	3	4	5	6	6a c	6b	7	8/10 d	8a c /10 d	9
GH stimulation (provocation) test y	X												
Morning cortisol (at 8am ±1am)	X												
ACTH or CRH stimulation test z	X												

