**LT-OLE:**

Study Procedure	LT-OLE – Year 1					
	LT-OLE 10 (+4) a					
Study Day (± in dy/s)						
Study Wk (± in wk/s)	54	56 (+2)	65 (±2)	78 (±2)	91 (±2)	104 (±4) b
Study Month	12.5	13 c	15	18	21	24
Study Visit	11 d	12	13	14	15	16
Auxology measurements e			X	X	X	X
Physical examination and vital signs f		X	X	X	X	X
ECG						X g
Pubertal status (Tanner stages)						X
Urine pregnancy test for girls reporting 1 st menstrual cycle		X	X	X	X	X
BA (Greulich-Pyle method using central BA reader)						X
Dispense study drug		X	X	X	X	X
Individual dose adjustment			X	X	X	X
Diary card return		X	X	X	X	X
Local tolerability	X	X	X	X	X	X
AEs	X	X	X	X	X	X
Prior & concomitant medications	X	X	X	X	X	X
MOD-4023 IP return		X	X	X	X	X
Fundoscopy	ONLY if there are signs or symptoms indicative of benign intracranial hypertension					
Laboratory Assessments						
Hematology h , chemistry i , & urinalysis j			X	X		X

a If visit occurs on dosing day (day 14), procedures should be performed prior to dosing.

b Pre- and post- dose assessments may be performed on separate days that will be appropriately recorded in the EDC.

c For Genotropin® patients that switch to MOD-4023 only. For existing MOD-4023 patients: AE and concomitant medication review only by phone interview.

d For Genotropin® patients that switch to MOD-4023 only.

e Actual Ht (mean of 3 consecutive measurements per patient per visit) measured on a calibrated wall mounted stadiometer.

f Body weight, ideally fasted in the morning, without shoes and having removed all outwear and heavy pocket items.

g ECG will be conducted at 7-12 hours post-dose.

Effective Date: Date of final electronic approval

Study Procedure	LT-OLE – Year 1					
	LT-OLE 10 (+4) a					
Study Day (± in dy/s)						
Study Wk (± in wk/s)	54	56 (+2)	65 (±2)	78 (±2)	91 (±2)	104 (±4) b
Study Month	12.5	13 c	15	18	21	24
Study Visit	11 d	12	13	14	15	16
IGF-1, IGF-1 SDS, IGFBP-3, and IGFBP-3 SDS		X	X	X	X	X
MOD-4023 serum levels	X	X	X	X	X	X
Thyroid function (TSH, fT4)			X	X		X
Glucose metabolism k			X	X		X
Lipid profile l			X	X		X
LH, FSH and testosterone m						X
LH, FSH and estradiol n						X
Abs to MOD-4023	X	X	X	X	X	X

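### Appendix A omits the Visit 12 safety laboratory panel that Section 5.3.2 and the synopsis require for children switching from Genotropin to MOD-4023

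*Protocol*

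**What the plan says.** Section 5.3.2 covers Visit 12 for switchers and introduces its list with "The following assessments will be conducted at Visit 12 on Day 4 (-1) post dose". The list includes "Safety laboratory tests: chemistry, hematology and urinalysis". The synopsis repeats the same item in its Visit 12 list for switchers.

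In the Appendix A table for LT-OLE Year 1, the columns are Visits 11 to 16. The row "Hematology h , chemistry i , & urinalysis j" is marked at Visits 13, 14 and 16 only. A footnote on the Visit 12 column limits the full visit to switchers; for the others it says "For existing MOD-4023 patients: AE and concomitant medication review only by phone interview". No footnote adds the panel at Visit 12.

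On which source sets the timing, Section 5.8 states: "Physical examination and safety laboratory assessments will be performed according to the schedule of events in Appendix A". Section 5.8.9 also refers to the Appendix A schedule for routine laboratory tests, and SAP Section 3.5.2 defers to the protocol's schedule.

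**The concern.** Two operative parts of the current protocol give different instructions for the same visit, and the part to which sites are directed for laboratory timing is the incomplete one. Visit 12 carries the first routine chemistry, hematology and urinalysis panel scheduled after these children first receive MOD-4023. Where a site works from the table, that one-month check is lost.

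Section 8.6.6 rests the extension's safety assessment mainly on treatment-emergent adverse events and on laboratory values outside pre-set ranges. If some sites take the panel and others do not, the Month 13 laboratory data for switchers will be incomplete in a way that depends on site practice. It will also be unclear whether a missing panel counts as a protocol deviation.

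**Working it through.** The protocol states no figure to reproduce here. The check is a comparison of text and table, followed by simple arithmetic on the visit weeks.

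**1. Is the blank cell real?** Relevant rows of the LT-OLE Year 1 table, read against its Visit 11 to 16 header:

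| Row | V11 | V12 | V13 | V14 | V15 | V16 | Listed in 5.3.2 for V12? |
|---|---|---|---|---|---|---|---|
| Hematology, chemistry, urinalysis | – | – | X | X | – | X | **Yes** |
| Physical examination, vital signs | – | X | X | X | X | X | Yes |
| IGF-1 / IGFBP-3 | – | X | X | X | X | X | Yes |
| MOD-4023 serum levels | X | X | X | X | X | X | Yes |
| Antibodies to MOD-4023 | X | X | X | X | X | X | Yes |
| Thyroid, glucose, lipids (three rows) | – | – | X | X | – | X | No |

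Other rows are marked at Visit 12, so the column has not been lost or shifted. The thyroid, glucose and lipid rows are blank there, in agreement with the text. The safety panel is the laboratory row where text and table disagree. Its pattern is the same as those three rows, which suggests it was carried over with the Visit 13/14/16 block of Section 5.3.3. That explanation is an inference; the blank is not.

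**2. Is there an earlier post-switch panel?** No. Visit 11 (Section 5.3.1) has drug levels, antibodies, adverse events with local tolerability, and concomitant medication only. The Visit 8/10 panel is the end-of-main-study assessment. The repeat after more than 90 days off treatment is a re-entry baseline.

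**3. Which version is intended?** In the main study the same panel is taken at Visit 4, one month after first dose, and there Section 5.2.4 and Appendix A agree. This supports the text as the intended design.

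**4. Timing.** Assume that MOD-4023 starts at Week 52.

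- By the text, Visit 12 is Week 56: 56 − 52 = 4 weeks after the switch. The text's ±2-week window gives 2 to 6 weeks. Appendix A prints +2 weeks only, which gives 4 to 6.
- By the table, Visit 13 is Week 65 (±2): 65 − 52 = 13 weeks, range 11 to 15.
- Nominal delay: 65 − 56 = 9 weeks.

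In the text Visit 12 is tied to the first MOD-4023 dose, while Visit 13 is printed as Week 65. For a start at Week *s* the nominal delay is therefore 65 − (*s* + 4) = 61 − *s*: 9 weeks at *s* = 52 and 7 weeks at *s* = 54.

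**5. Number of children.** The planned Genotropin arm is 110, with about 10% dropout: 110 × 0.90 = 99 completers. If all continue and every site follows the table, 99 are affected; this is the ceiling. For illustration, assume that 80% to 100% of completers continue and that 25% to 50% of switchers are at sites following the table:

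- low: 99 × 0.80 × 0.25 = 19.8, about 20;
- high: 99 × 1.00 × 0.50 = 49.5, about 50.

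Neither assumption has a source in the documents.

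**The case against.** The strongest reply is that this is one missing X for one routine panel at one visit, with little at stake. The table still schedules physical examination, vital signs, adverse events, IGF-1, drug levels and antibodies at Visit 12. IGF-1 is the laboratory trigger for dose reduction in Section 6.4.1, and no dose rule names the routine panel. Section 5.6 allows unscheduled laboratory tests. The extension has no hypothesis testing. All of this stands and limits the consequence, but it does not make the two instructions agree.

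The comparison with Visit 4 is imperfect: those children had never received growth hormone, whereas switchers have had 12 months of daily treatment with safety panels through Visit 8. This is fair. Switchers are nonetheless at the same point after first exposure to MOD-4023, and the text asks for the panel regardless of the analogy.

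Section 5.3.2 is the visit-specific instruction and the synopsis backs it, so sites may well have followed the text. Section 5.8.9 also points to a Central Laboratory Manual that is not among the documents. Whether any child missed the panel therefore cannot be determined, and the figure of 20 to 50 is an illustration, not an estimate. That stands too.

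The 9 weeks are nominal and shrink with a later start, as shown above; Visit 8's own ±1-week window also moves the start. Finally, the SAP names no Month 13 laboratory table, and its list of tables is redacted. The expectation of by-visit laboratory results comes from the general wording of protocol Section 8.6.8.

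**Conclusion.** The concern holds. The protocol prescribes the panel at Visit 12 for switchers in two places and omits it from the schedule that governs laboratory timing. A site following Appendix A takes its first scheduled post-switch panel about 13 weeks after the switch instead of about 4, assuming a Week 52 start. The number of children affected is unknown, with a ceiling of about 99.

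This is a document inconsistency with a limited safety-monitoring consequence. It does not touch the non-inferiority comparison or the other scheduled Visit 12 measurements. It should be corrected because the omitted item is a safety check in children newly exposed to an investigational product, and because the correction is nearly free.

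**What to change.** In the LT-OLE Year 1 table of Appendix A, mark the hematology, chemistry and urinalysis row at Visit 12. The existing footnote c on that column already restricts the on-site visit to switchers, so no new footnote is needed. Notify sites, and confirm that the Visit 12 laboratory kits and the Central Laboratory Manual include the panel. If some children have already passed Visit 12, report how many switchers had the panel and how many did not, so that the Month 13 laboratory data can be read correctly.

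The cost is one table cell, a site notice and the added laboratory tests. Switchers already attend Visit 12 on site and have blood drawn, so no visit is added.
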